**REVISION HISTORY**

| Revision # | Version Date | Summary of Changes  | Consent Change? |
|-------------------|---------------------|--|------------------------|
| 2                 | 2.8.22              | Added [name] and [name]; removed [name] | No                     |
| 3                 | 6.27.22             | Added i2b2   | No                     |
| 4                 | 7.20.22             | Remove i2b2; added Consent2Share                                 | No                     |

## 1.0 Study Summary

|   |  |
|---|--|
| Study Title                                | Medical Marijuana Use and Driving Performance: A Test of Psychomotor Function in Adults 50 and Older   |
| Study Design                               | We will use a naturalistic observational trial design to compare psychomotor function at baseline (in the week prior to starting medical marijuana) as well as 1 month and 3 months post-medical marijuana initiation. |
| Primary Objective                          | Simulated driving performance (i.e., errors in response time, attention, and executive functioning tasks that predict on-road performance)   |
| Secondary Objective(s)                     | Adverse effects  |
| Research Intervention(s)                   | Medical marijuana  |
| Study Population                           | Adults 50 and Older  |
| Sample Size                                | 60   |
| Study Duration for individual participants | 3 months and 1 week  |
| Study Specific Abbreviations/ Definitions  | MMTC = Medical Marijuana Treatment Clinics of Gainesville  |

### 1.1 Abstract

1.1.1 Background: Approximately 6.9 million people in the State of Florida are aged 50 and older. Further estimates of chronic pain in this population ranges from 35-52%. Of the 33 states (including Florida) with laws that legalize marijuana for medical use, chronic pain, a condition with greater prevalence in mid to late life, is recognized as a common ailment for which physicians prescribe medical marijuana. However, little is known about marijuana use during late-middle age (ages 50–64) and older adulthood (ages 65 and older). While medical marijuana may benefit older adults by reducing pain, factors such as how use may affect everyday functioning during real world tasks such as driving is underexamined. To date, a study that examines older adults' pre-exposure to medical marijuana and systematically tracks medical marijuana initiation, dosage, and psychomotor functioning has not been done.

1.1.2 Method/Design: This protocol describes an assessment of Medical Marijuana Use and Driving Performance: A Test of Psychomotor Function in Adults 50 and Older. Sixty participants will be recruited from Medical Marijuana Treatment Clinics (MMTC) of Gainesville. The intervention group will be comprised of adults 50 and older who report severe or chronic pain, are newly registered for the Medical Marijuana Registry in the State

PROTOCOL TITLE: Medical Marijuana Use and Driving Performance: A Test of Psychomotor Function in Adults 50 and Older.

of Florida, have no prior history of medical marijuana use, can communicate in English, and are willing and able to complete study procedures. The control group will be age, gender, and race matched. The primary study outcome is simulated driving performance (i.e. errors in response time, attention, and executive functioning tasks that predict on-road performance). Secondary outcomes include adverse effects.

1.1.3 Expected Value: Currently, there is limited scientific data on how medical marijuana affects psychomotor functioning in real world situations among those 50 and older. Further, extant literature suggests that certain factors (i.e. dosage, frequency, CBD/THC content, and route of administration) may be associated with greater risk of adverse effects for older adults. While some evidence suggests that marijuana is beneficial for pain, other evidence suggests that marijuana use may be associated with slowed response time, poor attention, and poor executive functioning. Physicians, patients, and policy makers need data-driven guidelines for medical marijuana use in older adults, a prevalent population in the State of Florida. To that end, the National Institute on Drug Abuse has called for data on medical marijuana in adults 50 and older specifically. The long range goal of this work is to improve our understanding of the consequences of medical marijuana use in later life and to facilitate the development of best practice guidelines for adults 50 and older.

## 2.0 Objectives\*

2.1 The specific aims for the current project are:

**Aim1:** Test the association between medical marijuana use and driving errors that predict on-road performance on a high-fidelity driving simulator in adults 50 and older with chronic or severe pain.

**H1a:** We hypothesize that medical marijuana use will be associated with slower response time in a driving performance task.

**H1b:** We hypothesize that medical marijuana use will be associated with poorer divided attention in a driving performance task.

**H1c:** We hypothesize that medical marijuana use will be associated with poorer executive functioning in a driving performance task.

**Aim2:** Examine the association between medical marijuana use factors (dosage, frequency, CBD vs. THC products, and route of administration) and adverse effects in adults age 50 and older.

**H2a:** We hypothesize that higher dosage and frequency of administration will be associated with greater adverse effects.

**H2b:** We hypothesize that THC-based products will be associated with greater adverse effects.

**H2c:** We hypothesize that products administered by vaporizer will be associated with greater adverse effects.

PROTOCOL TITLE: Medical Marijuana Use and Driving Performance: A Test of Psychomotor Function in Adults 50 and Older.

### 3.0 **Background\***

3.1 Prevalence of marijuana use has increased 300% in the last 10 years among those 50 and older, and this upward trend is expected to continue. Marijuana initiation at age 50 and older has also increased exponentially due to changing cultural norms. In addition, prevalence estimates of chronic or severe pain in this population ranges from 35-52%, with some estimates as high as 74%. In the United States, chronic pain is the most frequently endorsed reason for medical marijuana use.

Current research indicates that marijuana users may experience cognitive impairment in areas such as attention, executive functioning, and psychomotor speed. Specifically, research has explored the effect of marijuana use on psychomotor skills, which are skills that combine thinking and movement. Researchers assessed psychomotor function on measures of critical tracking, attention, and reaction time, and findings indicated that cannabis usage created deficits in psychomotor function up to 3.5 hours after use, which is congruent with prior work. Impairments to psychomotor abilities have practical implications, as these impair an individual's ability to drive. In a study that evaluated psychomotor function using the same critical tracking and divided attention tasks, Bosker et al. (2013) examined whether psychomotor functioning would improve, following abstinence among chronic, daily cannabis users. Extending previous research, results of this study indicated that psychomotor function was impaired, but sustained abstinence (3 weeks) did improve psychomotor performance, which is consistent with other findings. However, psychomotor performance did not completely recover to a normal performance as based on the control group. Solowij & Pesa (2010) extended this conclusion by suggesting that long-term marijuana use is also associated with impaired attention, inhibition, working memory, and verbal memory. Furthermore, Nestoros & colleagues (2017) found that chronic, heavy cannabis use was related to general cognitive dysfunction. Some researchers suggest that the aforementioned cognitive impairments may be due to the extent of changes in CB1 stimulation, while other studies indicate that cannabis composition may influence the type/severity of the marijuana-related cognitive impairment. Together, this lack of consensus indicates that further work is needed to understand if medical marijuana use creates a long-term impact on psychomotor functioning that impact real world tasks such as response time, attention, and executive functions—all critical for the task of driving. Further, clarity is needed regarding whether specific factors of marijuana use are associated with greater adverse effects in this population.

Research on psychomotor functioning in older adults generally uses cognitive assessment tools such as the Trails Making test which have limited real world application. However, studies of driving performance using driving simulators have been shown to be a valid predictor of on-road driving performance. Driving simulators allow for the systematic presentation of events and the manipulation of variables, which offers experimental control that is impossible on the road. Driving simulators also offer optimal stimulus presentation which

**PROTOCOL TITLE:** Medical Marijuana Use and Driving Performance: A Test of Psychomotor Function in Adults 50 and Older.

allows for analysis of both healthy and impaired drivers under similar conditions. Therefore, using a driving simulator we can examine response time, attention, and executive functions using valid real world tasks. Research shows that crash patterns for older adults are different. Older adults are more likely to be involved in crashes at intersections or during merges, and these crashes are inherently more fatal. The challenging, fast-paced environment presented by intersections and merges puts extra demand on cognitive, sensory, and motor domains applicable to driving; therefore, slower response time, inattention, and difficulty with executive functions may lead to more fatal crashes. Therefore, how marijuana use influences driving performance needs to be examined, and the driving simulator is the safest option to do so.

## **4.0 Study Endpoints\***

### **4.1 Simulated Driving Performance**

Data will be collected via the kinematic functionality of the high-fidelity driving simulator (i.e., speed in mph, lateral lane positioning, braking, etc.) and also through observing the performance of the driver.

#### **4.1.1 Response Time**

Type: Primary

Time Frame: Baseline (T1), 1 Month (T2) and 3 Months (T3)

Brief Description: After the first 5-minute acclimation scenario, the driver will drive the main drive for another 15 minutes. The first 7 minutes of the drive will include daytime driving, start in a rural area with some ambient traffic, rolling hills, curves in the road, and include the occasional lead vehicle, oncoming traffic, and some vehicles behind the driver. Data will be collected via the kinematic functionality of the high-fidelity driving simulator (e.g. speed in mph, braking, swerving, lateral lane positioning, etc.) and also through observing the performance of the driver -- for yes/no responses – via a trained evaluator who will use the playback function of the simulator to scrutinize the errors. To assess response time, a vehicle is pulling out in front of the driver and the driver's behavior is measured via braking milliseconds (ms) and swerving (SD of lateral deviation from center lane).

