#### **4.1.2 Divided Attention**

Type: Primary

Time Frame: Baseline (T1), 1 Month (T2) and 3 Months (T3)

Brief Description: Data will be collected via the kinematic functionality of the high-fidelity driving simulator and observation. During the course of the main drive consisting of straight residential roadways connecting 8 left turns and 2 right turns with minimal ambient traffic using an established protocol, during the course of the drive divided attention (being aware of the traffic and surrounding while focusing on critical stimulus) is assessed

PROTOCOL TITLE: Medical Marijuana Use and Driving Performance: A Test of Psychomotor Function in Adults 50 and Older.

via a diamond on the screen turning to a triangle and the participant needs to honk (i.e. respond) as soon as (s)he sees it (measured in ms and number of omissions and commissions).

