#### 4.1.3 Executive Functions

Type: Primary

Time Frame: Baseline (T1), 1 Month (T2) and 3 Months (T3)

Brief Description: The last 8 minutes of the drive starts in a residential area with low speeds (15-30 mph) and then progresses to city with speeds 30-45 mph. This part of the drive will occur in a suburban environment, daytime driving with minimal lead, following and oncoming traffic, and some pedestrians and cyclists. Streets will be surrounded by buildings and strip malls. Executive functions are measured by providing the driver with an instruction before the drive (e.g. to turn into a McDonald's, pull into a parking bay, park the car (vehicle positioning), and when it is safe to do so, back up out of the parking bay (visual scanning) exit the lot and merge into the flow of traffic. Executive functions are measured via visual scanning (yes/no), speed regulation (mph over or under the speed limit), adjustment to stimuli (notice the McDonald's (yes/no), slow down (mph), signaling (yes/no), vehicle positioning (buffer around the vehicle yes/no), and gap acceptance (narrow or tight via ms).

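### The plan does not say that the evaluator who scores the yes/no executive-function items from playback is masked to group or visit, which leaves part of H1c open to expectation bias

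*Combined protocol and SAP*

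**What the plan says.** Section 4.1 takes the driving endpoints from the simulator's kinematic record "and also through observing the performance of the driver". Section 4.1.1 adds that yes/no responses are obtained "via a trained evaluator who will use the playback function of the simulator to scrutinize the errors".

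The three primary domains differ in how far they depend on a person's judgement:

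- **Response time (H1a), section 4.1.1:** "measured via braking milliseconds (ms) and swerving (SD of lateral deviation from center lane". Both are instrument measures.
- **Divided attention (H1b), section 4.1.2:** "measured in ms and number of omissions and commissions". The section also lists observation as a data source, without saying what is observed.
- **Executive functions (H1c), section 4.1.3:** four yes/no items, namely "Executive functions are measured via visual scanning (yes/no"), "adjustment to stimuli (notice the McDonald's (yes/no"), and "signaling (yes/no), vehicle positioning (buffer around the vehicle yes/no"). Speed regulation, slowing down and gap acceptance are numeric.

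H1c in section 2.0 is directional: "We hypothesize that medical marijuana use will be associated with poorer executive functioning in a driving performance task".

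Section 6.3 covers staff training, a private setting and reminders about confidentiality. Section 17.8 codes data to protect identity. No section provided mentions hiding group or visit from the evaluator, shuffling recordings, or keeping the evaluator apart from the staff who run visits.

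**The concern.** Exposure in this study is observed and not concealed. Users come from marijuana clinics and controls from the community (sections 6.1 and 23-type recruitment text within 6.1). Users are asked about problems since starting marijuana (section 6.8), and section 17.7 mentions a urine test for THC. Anyone who runs visits will readily know a participant's group and how far along that participant is.

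Whether a driver scanned adequately, noticed the target or left enough room is partly a judgement. A scorer who knows group and visit and expects impairment may settle doubtful cases in that direction. A lean that was constant across all visits would cancel in change from baseline. A lean at T2 and T3 only would not, and neither kind cancels in the direct group comparisons planned in section 17.1. What is at stake is an apparent effect on the judged part of one primary domain that comes from scoring and not from driving.

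**Working it through.** **The plan's own figure.** Section 17.4 assumes a correlation of 0.2 over three time points. The SD multiplier is sqrt((1 + 2 × 0.2)/3) = 0.683, as stated. For a difference of 0.5 SD, two-sided, with 80% power and an assumed alpha of 0.05 (not stated), the t-test solution is 30.28, which rounds up to the stated 31 per group. The figure reproduces. It says nothing about scoring bias, so what follows is illustrative.

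**Inputs from the documents.** 30 per group (section 6.1); four yes/no items (section 4.1.3); three visits, two of them after initiation; correlation 0.2 (section 17.4).

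**Assumed inputs.** A true error rate of 20% in both groups, so no real effect. A lean b of 5 or 10 percentage points in errors recorded for users, at T2 and T3 only. The plan's 0.2 is a correlation between visits; using it between items within one drive as well is a further assumption.

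**Formulas.** With k scores per person:

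- design effect = 1 + (k − 1) × 0.2
- effective n per group = 30k / design effect
- d = expected recorded difference: b for T2+T3, or b × 2/3 for the three-visit average
- z = d / sqrt([0.20 × 0.80 + (0.20 + d)(0.80 − d)] / effective n)
- false-positive rate = Φ(z − 1.96) + Φ(−z − 1.96)

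| Analysis | k | Design effect | Effective n | z at b = 5, 10 points | False-positive rate |
|---|---|---|---|---|---|
| One item, three-visit average | 3 | 1.4 | 64.3 | 0.46, 0.90 | 7%, 15% |
| Four items, three-visit average | 12 | 3.2 | 112.5 | 0.61, 1.19 | 9%, 22% |
| Four items, T2+T3 pooled | 8 | 2.4 | 100 | 0.85, 1.64 | 14%, 38% |

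Worked example, four items over T2+T3 with b = 5 points: z = 0.05 / sqrt((0.16 + 0.1875)/100) = 0.05/0.0589 = 0.85, and Φ(−1.11) + Φ(−2.81) = 0.136.

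**Cross-checks.**

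- Exact enumeration for one item at one visit, 30 per group, 20% true rate: 4.9% with no lean, 7.3% at 5 points and 14.2% at 10 points.
- Simulation of the four-item sum over T2+T3 (40,000 runs, Welch t-test, correlation 0.2, 20% true rate): 4.7% with no lean, 13.1% at 5 points and 36.4% at 10 points.
- Varying the true rate from 20% to 40% and the correlation between 0 and 0.2 in that simulation widens the ranges to 11–25% at 5 points and 29–70% at 10 points.
- If signalling is logged by the simulator, three judged items over T2+T3 have k = 6, design effect 2.0 and effective n 90, which gives 13% and 34%.

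**The case against.** **Silence is not open scoring.** A reader might infer that the plan requires scoring with group and visit known. It does not say so. It does not state who the evaluator is, whether that person meets participants, or how recordings are labelled. A figure in section 6.11 is not shown, and section 18.1 refers to a human-subjects document that was not provided; masking could be described in either. This stands. The coding in section 17.8 does not settle the matter, because it protects identity and a subject code need not hide group or visit.

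**Four judged items may be too many.** The evaluator sentence is in 4.1.1, and 4.1.3 names no evaluator. Applying it there is a reasonable reading, since that is where the yes/no items are listed. Section 6.7 treats signalling as a cab control whose inputs pass through software, so that item may need no judgement. This also stands.

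**The largest figures come from a test the plan does not contain.** Section 17.1 specifies group comparisons and repeated-measures ANOVA over all three time points, section 17.4 powers a three-visit average, and no rule combines the items. The 14% to 38% therefore cannot be read as the study's error rate; the lower rows of results belong beside it.

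**The bias is not beyond repair.** A reader might infer that no analysis could help. The numeric executive-function measures allow a comparison free of judged items, and masked rescoring is possible if recordings are kept. What remains is that the planned tests, applied to the judged scores alone, cannot separate a lean from a real effect.

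**Conclusion.** The point holds in a limited form. The plan has yes/no items scored by a person from playback, places such items in a primary endpoint with a directional hypothesis, and does not state that the scorer is masked to group or visit. Nothing in the text provided prevents expectation from entering those scores; nothing shows that it will.

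The exposure covers the judged items within H1c: visual scanning, noticing the target and the vehicle buffer, with signalling doubtful. It does not reach the numeric executive-function measures, and H1a and H1b are largely protected.

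Under the assumed values, false-positive rates run from about 7% for one item with a 5-point lean to 38% for a four-item T2+T3 pool with a 10-point lean, against a nominal 5%. These rest on an assumed error rate, an assumed lean with no source in the documents, and, for the four-item results, a composite the plan does not define. The change is worth making because scoring already uses recordings.

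**What to change.** Add to sections 4.1.1 and 4.1.3:

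- Playback files carry random codes that hide group and visit.
- The planned trained evaluator scores them in shuffled order.
- Scores are locked before codes are linked to group and visit.
- Where existing staffing allows, each recording goes to a trained evaluator who did not run that participant's visits.

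In the analysis, report speed regulation, slowing and gap acceptance separately from the judged items. If masking is already described in a document not provided here, a cross-reference is enough.

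The cost is file handling and later scoring, since recordings must be batched across groups and visits. The recordings and participant procedures stay the same. Requiring in every case an evaluator who ran no visits could need extra staff, which is why that step is conditional.

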#### **4.1.2 Divided Attention**

Type: Primary

Time Frame: Baseline (T1), 1 Month (T2) and 3 Months (T3)

Brief Description: Data will be collected via the kinematic functionality of the high-fidelity driving simulator and observation. During the course of the main drive consisting of straight residential roadways connecting 8 left turns and 2 right turns with minimal ambient traffic using an established protocol, during the course of the drive divided attention (being aware of the traffic and surrounding while focusing on critical stimulus) is assessed

PROTOCOL TITLE: Medical Marijuana Use and Driving Performance: A Test of Psychomotor Function in Adults 50 and Older.

via a diamond on the screen turning to a triangle and the participant needs to honk (i.e. respond) as soon as (s)he sees it (measured in ms and number of omissions and commissions).

#### 4.1.3 Executive Functions

Type: Primary

Time Frame: Baseline (T1), 1 Month (T2) and 3 Months (T3)

Brief Description: The last 8 minutes of the drive starts in a residential area with low speeds (15-30 mph) and then progresses to city with speeds 30-45 mph. This part of the drive will occur in a suburban environment, daytime driving with minimal lead, following and oncoming traffic, and some pedestrians and cyclists. Streets will be surrounded by buildings and strip malls. Executive functions are measured by providing the driver with an instruction before the drive (e.g. to turn into a McDonald's, pull into a parking bay, park the car (vehicle positioning), and when it is safe to do so, back up out of the parking bay (visual scanning) exit the lot and merge into the flow of traffic. Executive functions are measured via visual scanning (yes/no), speed regulation (mph over or under the speed limit), adjustment to stimuli (notice the McDonald's (yes/no), slow down (mph), signaling (yes/no), vehicle positioning (buffer around the vehicle yes/no), and gap acceptance (narrow or tight via ms).

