PROTOCOL TITLE: Medical Marijuana Use and Driving Performance: A Test of Psychomotor Function in Adults 50 and Older.

visual channels form an immersive and realistic driving experience. A 5.1 channel audio system external to the car cab provides the environmental sounds such as traffic, passing vehicles, and road noise. An internal audio system to the car cab provides the engine sounds and vibrations, as well as pre-programmed voice commands and any other scripted sounds. A 4-door sedan allows the driver to operate normal accelerator, brake, steering, transmission selection, and signaling controls with the simulator responding accordingly. All driver inputs are controlled by software that interfaces with the electronics in the car cab. The adaptation scenario is standardized for older adults and has been used in our prior driving studies. The main drive consists of straight residential roadways connecting 8 left turns and 2 right turns with minimal ambient traffic. Three scripted events will be randomly presented to the drivers. To assess response time, a vehicle is pulling out in front of the driver and the driver's behavior is measured via braking (ms) and swerving (SD of lateral deviation from center lane). Next, divided attention is assessed via a diamond on the screen turning to a triangle and the participant needs to honk as soon as (s)he sees it (measured in ms and number of omissions and commissions). Lastly, executive functions are measured by providing the driver with an instruction before the drive (i.e. to turn into a McDonald's, pull into a parking bay, and when it is safe to do so, exit the lot and merge into the flow of traffic (measured via visual scanning (yes/no) speed regulation (mph over or under the speed limit), adjustment to stimuli (notice the McDonald's (yes/no), and slow down (mph), signaling (yes/no), vehicle positioning (buffer around the vehicle yes/no), and gap acceptance (narrow or tight via m/sec).

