## **17.0 Data Management\* and Confidentiality**

17.1 **Test of Aim 1 (Driving Simulator):** Between group (medical marijuana users vs controls) comparisons will first be examined using independent samples t-test (controlling for unequal variances using Levene's test) or Mann-Whitney U tests if the data are nonparametric. Repeated measures ANOVA will be used to examine within participants differences on measures at all 3 time points in order to answer the question of whether medical marijuana impacts response time, divided attention, and executive functions.

Limitations may be related to the distribution of the dependent and independent variables. Possible mitigation approaches include creating a dichotomous variable of high versus low for outcomes and using logistic regression or other functional form as dictated by the distribution of the dependent and independent variables.

17.2 **Test of Aim 2 (Adverse Effects):** To describe factors associated with adverse effects we will report the number of adverse effects reported by participants at time points 2 and 3. Adverse Effects will be defined as both a count variable and a binary variable such that absence or presence of adverse effects will be coded as 0/1 respectively. We will then use Poisson and Logistic regression methods to examine analyze the bivariate association between dosage, frequency of use, route of administration (pills, vape, etc.), and type of product (THC v. CBD). Limitations may be related to the frequency and distribution of events leading to complete or quasi-separation of data points. Possible mitigations would be re-categorization of explanatory variables, exact or firth regression, or a different functional form of the model. The goal of aim 2 is to examine the strength of the association between factors of medical marijuana use and adverse effects. As there may be insufficient power for statistical

PROTOCOL TITLE: Medical Marijuana Use and Driving Performance: A Test of Psychomotor Function in Adults 50 and Older.

significance, effect size estimates (Cohen's d) will be used to examine the strength of the association between variables.

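### Three domains are labelled primary and list about 10 to 12 measures, but no measure or score is named to decide H1b or H1c, and no alpha or multiplicity rule is stated.

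*Combined protocol and SAP*

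**What the plan says.** Section 1.1.2 describes one outcome: "The primary study outcome is simulated driving performance (i.e. errors in response time, attention, and executive functioning tasks that predict on-road performance". Section 4 then labels three domains primary, each at T1, T2 and T3, and lists several measures under each:

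- Response time (4.1.1, H1a), two measures: "braking milliseconds (ms) and swerving (SD of lateral deviation from center lane".
- Divided attention (4.1.2, H1b), three measures: "measured in ms and number of omissions and commissions".
- Executive functions (4.1.3, H1c): "Executive functions are measured via visual scanning (yes/no), speed regulation (mph over or under the speed limit), adjustment to stimuli" (noticing the target and slowing down), then signaling, vehicle positioning and gap acceptance. That is seven items, four of them yes/no.

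The total is 12. It is 11 if noticing and slowing down form one item, as section 6.7 suggests ("adjustment to stimuli (notice the McDonald's (yes/no), and slow down (mph"), and 10 if omissions and commissions are also taken together.

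The hypotheses in section 2.1 are directional and name domains. H1a, for instance, is that "medical marijuana use will be associated with slower response time in a driving performance task".

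For Aim 1, section 17.1 gives t-tests or "Mann-Whitney U tests if the data are nonparametric" between groups, and repeated measures ANOVA across the three visits. If distributions are awkward, it lists as possible mitigation a high/low split with logistic regression, or another functional form. It gives no cut-point and no rule for switching.

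Section 17.4 computes power for one two-sided comparison of a three-visit average. No alpha, hierarchy or multiplicity rule appears in the document.

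**The concern.** A directional hypothesis needs a rule, fixed in advance, for what counts as support. H1b could rest on any of three results and H1c on any of six or seven, and nothing prevents that choice from being made after the data are seen. Section 1.1.3 wants the results to inform guidance for physicians, patients and policy makers, so false support for impairment would matter.

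The power section does not settle the question. Its effect size comes from total driving errors and lane-maintenance errors in an earlier study, and the plan defines neither as the score for any of H1a to H1c. The open fallback adds a second choice: a split with an unstated cut-point can be placed after inspection, and it discards information.

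**Working it through.** **1. The plan's own figure.** Inputs from section 17.4: effect 0.5 SD of one measure, correlation 0.2 across three visits, two-sided, 80% power. The SD of the average is √((1 + 2×0.2)/3) = 0.683, as stated. The standardised difference is 0.5/0.683 = 0.732. With alpha 0.05 (assumed), the two-sample noncentral t gives 80.9% at 31 per group, so the stated 31 is reproduced, and 79.6% at the 30 per group in section 6.1. By the normal approximation, two-sided 0.10 would need 24 per group and two-sided 0.01 would need 44. The calculation therefore implies 0.05 for a single test and leaves no room for multiplicity.

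**2. Chance of at least one false positive.** Assumptions, none of them in the plan: two-sided 0.05 for each measure, one test per measure, equal correlation of 0.2 to 0.5 between measures. Normal statistics were simulated (400,000 draws) with rejection at |z| > 1.96.

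| Tested | Any direction (correlation 0.2 to 0.5) | Toward impairment only |
|---|---|---|
| 12 measures | 43% to 32% | 22% to 16% |
| 10 measures | 38% to 29% | 20% to 14% |
| H1c, 7 items | 29% to 23% | 15% to 12% |
| H1c, 6 items | 25% to 21% | 13% to 10% |
| H1b, 3 measures | 14% to 12% | – |

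Independence is the upper bound: 1 − 0.95^12 = 46% for 12 measures.

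These rows treat every item as continuous. If the four yes/no items use Fisher's exact test, which is conservative at 30 per group, with 15% failures assumed, the figures fall to about 36% to 28% for 12 measures and 20% to 17% for H1c with seven items.

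With one deciding measure per hypothesis the bound is 1 − 0.95^3 = 14.3%, or 1 − 0.975^3 = 7.3% toward impairment.

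**3. What a split costs.** A median split gives the same groups on the raw and the log scale. If the log of a skewed measure is roughly normal, the split can therefore be compared with a log-scale test using normal theory. As an illustration at a standardised difference of 0.732, a pooled-median cut leaves Φ(0.366) = 0.643 against 0.357 above the cut. By the normal approximation at 30 per group, power falls from about 81% to about 60%; the split would need 47 per group. With a cut at the control group's 90th percentile, power is 46%, so the unstated cut-point matters too.

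**4. Power for a contrast that answers the question.** The average in section 17.4 includes T1, which precedes exposure. Take instead the mean of T2 and T3, adjusted for T1, with correlation 0.2 and a 0.5 SD effect at T2 and T3. The variance is (1 + 0.2)/2 − 0.2² = 0.56, so d = 0.5/√0.56 = 0.668. At 30 per group, power is 72% at 0.05 and 55% at 0.05/3. Reaching 80% would take 37 and 49 per group respectively. With unadjusted change from T1, the variance is 0.6 + 1 − 0.4 = 1.2, d = 0.456, and power is 41% and 25%.

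**The case against.** Several counter-arguments have force.

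- **H1a is not really open.** Only braking time can be slower; lateral deviation cannot. This stands. What remains for H1a is that the plan does not say so.
- **The plan does not commit to splitting.** The split is one example in an open list that also allows another functional form, and Mann-Whitney is named for the between-group comparison. This stands. The fault is lack of specification, and Mann-Whitney is not extended to the repeated-measures analysis. Under strong skew a split can also match an untransformed analysis, so the fair comparison is with rank or log-scale methods.
- **Yes/no items make the inflation smaller.** This stands, and the lower figures are given above.
- **Family-wise control is not obligatory** for three separately reported hypotheses in an observational study. This stands; it is a choice, but one the plan should state.

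A reader might also infer that the investigators intend to test every measure and claim support from any one. The documents do not say that; the percentages show what the silence permits. Nor do they say that visits would be pooled as if independent or that the best of several cut-points would be chosen, so neither is charged against the plan. Finally, ANOVA on yes/no items fits poorly, but no inflation of the error rate was shown for it.

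**Conclusion.** The concern holds as a gap in specification, worth correcting cheaply. H1b and H1c have no deciding measure or score, H1a's is only implied, and alpha and the multiplicity position are missing. If all listed measures were tested, the chance of at least one false positive would be roughly 28% to 43% for 12 measures and 17% to 29% for H1c with seven items, depending on the correlation and on how yes/no items are tested. Naming one measure per hypothesis brings the total to at most 14% without any formal adjustment. These figures rest on an assumed alpha of 0.05, correlations of 0.2 to 0.5 and, for the lower values, 15% failures.

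The split is a lesser point: it is optional in the plan but inferior to available alternatives. The stronger readings, that all three hypotheses are equally undefined, that dichotomising is the planned analysis, or that lack of family-wise control is in itself an error, are not supported.

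**What to change.** Before data are seen:

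- **Section 4.1:** name one deciding measure or pre-defined score per hypothesis and label the rest supportive. Examples are braking time for H1a, response time to the symbol change for H1b and, for H1c, an average of standardised items with the worse direction fixed for each. Speed regulation needs particular care, because it is recorded both over and under the limit.
- **Sections 4.1.3 and 6.7:** reconcile the gap-acceptance unit, which is ms in the former and "gap acceptance (narrow or tight via m/sec" in the latter.
- **Section 17.1:** state alpha. Replace the high/low split with a log-scale or rank-based analysis for skewed deciding measures. Name one group contrast, such as the baseline-adjusted difference averaged over T2 and T3.
- **Multiplicity:** say either that the three hypotheses are tested without family-wise control (up to 14% for any false positive) or that Holm is used, and word conclusions to match.
- **Section 17.4:** restate power for the chosen contrast.

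The cost is wording in sections 4.1, 6.7, 17.1 and 17.4. The other measures become supportive, and the stated power is less favourable: for the baseline-adjusted contrast, 72% at 0.05 and 55% at 0.05/3. Holm lies between these, averaging about 63% to 64% per hypothesis if all three effects are real. Openly stated testing without family-wise control costs no power beyond the 72%.
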